4.1.4 Dose-expansion phase

During dose-expansion, patients will be monitored for safety according to the same criteria employed during the dose-finding phase (although events will not be considered DLTs during dose-expansion). Additionally, 4 cycles of safety information are required prior to opening the initial dose-expansion cohorts. See Section 4.1.2 for stopping criteria.

The dose-expansion phase will be conducted using a Simon 2-stage optimal design with an additional provision to include 1 mixed disease cohort (other malignant solid tumors).

Once the RP2D has been established, patients will be recruited to each of the following cohorts:

1. SARCOMA (bone sarcomas: osteosarcoma and Ewing sarcoma; soft-tissue sarcomas [$\geq 40\%$ of enrollment]: rhabdomyosarcoma, non-rhabdomyosarcoma, and other sarcomas)
2. STO (other solid tumors).

For the SARCOMA cohort, the initial stage will allow 11 evaluable patients, to be dosed in this disease-specific cohorts. If 2 or more responses in either of these cohorts are observed, additional patients will be accrued, as part of the second stage, into the corresponding expansion cohort; 15 patients will be accrued into the SARCOMA expansion cohort for a total of 26 evaluable patients. If there has been ≤ 1 objective response in either cohort, at the time that evaluable patients (11 patients) dosed in the initial stage who have been followed for at least 3 cycles have been assessed, the cohort will be discontinued for lack of benefit.

For the STO cohort, 10 evaluable patients will be enrolled into this mixed-disease cohort; Simon rules are not applicable for this cohort.

4.1.5 Study Conduct Mitigation During Study Disruptions Due to Cases of Civil Crisis, Natural Disaster, or Public Health Crisis

The guidance given below supersedes instructions provided elsewhere in this clinical study protocol (CSP) and should be implemented only during cases of civil crisis, natural disaster or public health crisis (eg, during quarantines and resulting site closures, regional travel restrictions, and considerations if site personnel or study participants become infected with severe acute respiratory syndrome coronavirus 2 [SARS-CoV-2] or similar pandemic infection), which would prevent the conduct of study-related activities at study sites, thereby compromising the study site staff or the participant's ability to conduct the study. The Investigator or designee should contact the study Sponsor to discuss whether the mitigation plans below should be implemented.

To ensure continuity of the clinical study during a civil crisis, natural disaster, or public health crisis, changes may be implemented to ensure the safety of study participants, maintain compliance with Good Clinical Practice (GCP), and minimize risks to study integrity. Where

allowable by local health authorities, ethics committees, health care provider guidelines (eg, hospital policies) or local government, these changes may include the following option:

- Obtaining consent for the mitigation procedures (note, in the case of verbal consent, the informed consent form [ICF] should be signed at the participant's next contact with the study site).
- Rescreening: Additional rescreening for screen failure and to confirm eligibility to participate in the clinical study can be performed in previously screened participants. The Investigator should confirm this with the designated medical monitor.
- Telemedicine visit: Remote contact with the participants using telecommunications technology including phone calls, virtual or video visits, and mobile health devices.

For further details on study conduct during civil crisis, natural disaster, or public health crisis, refer to [Appendix K](#).

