Radiological efficacy assessments ^u	X	On-study efficacy assessments occur every 8 weeks ± 1 week (always relative to the date of first dose), until radiological progression plus an additional regularly scheduled follow-up scan. This schedule MUST be followed regardless of any delays in dosing. For patients who achieve an objective response (CR, PR) or stable disease, and for whom the response is still evident at 12 months, subsequent tumor assessments are to occur every 16 weeks. Unscheduled assessments can be performed at any time during the study, as clinically indicated, based on signs and symptoms							8.1

Note: All assessments on treatment days are to be performed prior to infusion, unless otherwise indicated.

Note: Patients who restart combination therapy (having subsequently progressed on durvalumab monotherapy following the completion of 4 months of combination therapy) should complete the same assessments starting from Cycle 1 Day 1 of the dose-expansion phase, with the exception of PK, ADA, tumor biopsies, blood for CCI analysis, blood for CCI sequencing, and CCI.

^a Visit windows are relative to the first day of each cycle.

^b Written informed consent/assent and any locally required privacy act document authorization must be obtained prior to performing any protocol-specific procedures, including screening/baseline evaluations. If laboratory or imaging procedures were performed for alternate reasons prior to signing consent, these can be used for screening purposes with consent of the patient's parent(s)/legally authorized representative(s). However, all screening laboratory assessments must have been obtained within 28 days of Cycle 1 Day 1 and imaging/staging examination results must have been obtained within 21 days of Cycle 1 Day 1. The unique enrollment code will be obtained after ICF signature, through the IRT/RTSM.

^c Any clinically significant abnormalities detected require a confirmatory ECG result.

^d Tobacco use will be collected at the Investigator's discretion.

^e Serum or plasma clinical chemistry (including LFT monitoring) and hematology may be performed more frequently if clinically indicated.

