- ^q Blood sample for antibody titer measurement will be taken from all patients at C1D1 and from at least 14 patients on durvalumab plus tremelimumab combination therapy. At Cycle 1 Day 1, samples will be collected before tremelimumab infusion. Afterwards, a new sample should be collected at least 4 weeks after a vaccine has been given and end of treatment visit. Upon confirmation that a sufficient number of samples has been successfully analyzed, sites will be informed so that further collection of samples can be discontinued.
- ^r Blood samples for CCI will be collected for at least 10 patients receiving durvalumab plus tremelimumab combination therapy.
- ^s See Section 8.8.1 for details around collection, requirement, and exemption for CCI.
- ^t The following tumor markers will be assessed in this study: alpha-fetoprotein for patients with hepatoblastoma and CCI for patients with germ cell tumors.
- ^u See Section 6.1.4 and Section 8.1 for additional details. Imaging modalities appropriate for the tumor type under consideration should be performed and the corresponding objective criteria used to monitor efficacy: solid tumors (RECIST 1.1 [Appendix E]). Confirmatory scans will be required.

ADA Anti-drug antibody; AE Adverse event; C Cycle; CR Complete response; CSF Cerebrospinal fluid; D day; Durva Durvalumab; ECG Electrocardiogram; FFPE Formalin-fixed paraffin-embedded; HIV Human immunodeficiency virus; ICF Informed consent form; IM Intramuscular; IP Investigational product; Interactive Response Technology (IRT); Randomization and Trial Supply Management (RTSM); LFT Liver function test; LP Lumbar puncture; CCI; NA Not applicable; CCI; PK Pharmacokinetics; PR Partial response; qXw Every X weeks; RECIST Response Evaluation Criteria In Solid Tumors; SAE Serious adverse event; CCI; Tremel tremelimumab; T3 Triiodothyronine; T4 Thyroxine; CCI; TSH Thyroid-stimulating hormone; W Week.

Table 3 Schedule of activities for patients who have discontinued all study treatments (durvalumab monotherapy or durvalumab and tremelimumab combination therapy) in the dose-finding or the dose-expansion phases

	Time since last dose of IP				For details, see Section
	Day (± 3)	Months (± 1 week)			
	30	2	3	4 months and every 2 months thereafter (± 2 weeks)	
Evaluation					
Physical examination (full)	X				8.2.1
Vital signs (temperature, respiratory rate, blood pressure, pulse, and peripheral oxygen saturation)	X	X	X		8.2.3
Weight	X	X	X		8.2.1
Pregnancy test ^a	X	X	X		8.2.1

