For the SARCOMA cohort, the initial stage will allow 11 evaluable patients, to be dosed in this disease-specific cohort. If 2 or more responses in either of these cohorts are observed, additional patients will be accrued, as part of the second stage, into the corresponding expansion cohort; 15 patients will be accrued into the SARCOMA expansion cohort for a total of 26 evaluable patients. If there has been ≤ 1 objective response in the SARCOMA cohort (11 patients), at the time that evaluable patients dosed in the initial stage have been followed/assessed for at least 3 cycles, the cohort will be discontinued for lack of benefit.

For the STO cohort, 10 evaluable patients will be enrolled into this mixed-disease cohort; Simon rules are not applicable for this cohort.

Study period:

Date of first patient enrolled: Q1 2019.

Estimated date of last patient completed: Q1 2023.

Number of patients:

Dose-finding phase: The final sample size in the dose-finding phase will depend on the number of DLTs and on the number of DLs to be explored. In addition, any patients not evaluable will be replaced in order to have the required number of patients evaluable at each DL. A minimum of 12 patients is anticipated to be dosed, to enable exploration of one DL in both patients weighing 35 kg and greater, and patients weighing under 35 kg. If all 3 DLs are used at both weight-based arms, then 36 evaluable patients would be necessary to complete the dose-finding phase. If approximately 20% of patients need to be replaced due to non-evaluability, then a maximum of 45 patients will be enrolled on the dose-finding cohorts.

Dose-expansion phase:

- Following a Simon 2-stage optimal design, a total of 26 evaluable patients (11 evaluable patients in the initial stage and an additional 15 patients in the second stage), are expected to be enrolled in the SARCOMA cohort.
- The STO cohort is planned to recruit 10 evaluable patients.

With the above considerations, the sample size for evaluable patients in the dose-expansion phase is expected to range from 38 to 66. Assuming that about 20% of patients may not be evaluable for objective response rate (ORR), the total number of patients dosed in the dose-expansion phase may range from approximately 46 to 80.

Screen failures are patients who do not fulfill the eligibility criteria for the study, and therefore must not be dosed. Patients may be rescreened a single time.

Treatments and treatment duration:

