9.2 Sample size determination

Dose-finding phase

The final sample size in the dose-finding phase will depend on the number of DLTs and on the number of DLs to be explored. In addition, any patients not evaluable (NE) will be replaced in order to have the required number of patients evaluable at each DL. A minimum of 12 patients is anticipated to be dosed, to enable exploration of 1 DL in both patients weighing 35 kg and greater, and patients weighing under 35 kg. If all 3 DLs are used at both weight-based arms, then 36 evaluable patients would be necessary to complete the dose-finding phase. If approximately 20% of patients need to be replaced due to non-evaluability, then a maximum of 45 patients will be enrolled on the dose-finding cohorts.

Dose-expansion phase

For the dose-expansion phase, the SARCOMA cohort mentioned in Section 4.1.4 will follow a Simon 2-stage optimal design. An ORR $\leq 10\%$ will not be considered clinically meaningful.

In the SARCOMA cohort, the Simon 2-stage design will have a type I error rate set at 0.1 (1-sided) and power of at least 85%. Based on the assumption that the ORR for the null hypothesis is 10% and the true ORR for the SARCOMA cohort is 30%, then the SARCOMA cohort will require a total of 26 evaluable patients (with the requirement that $\geq 40\%$ of the patients enrolled must have soft-tissue sarcomas), with 11 evaluable patients required in the first stage. If fewer than 2 responses are observed in the first 11 evaluable patients, then the cohort will be closed for lack of benefit. If 2 or more responses are observed out of the first 11 evaluable patients, then an additional 15 evaluable patients will be enrolled, for a total of 26 evaluable patients.

For a cohort that enrolls the maximum total of evaluable patients for that particular cohort (26 patients in the SARCOMA cohort), if fewer than 5 responses are observed out of the maximum total of evaluable patients, then no further investigation of this cohort will be done; if 5 or more responses are observed out of the maximum total of evaluable patients, then the null hypothesis will be rejected for this cohort and further investigation will be warranted.

The STO cohort is planned to recruit 10 evaluable patients. This sample size is based on practical, rather than formal considerations, as no formal hypothesis testing is planned for this cohort.

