Once the RP2D has been established, recruitment into the dose-expansion study will be conducted using a Simon 2-stage optimal design with an additional provision to include 1 mixed disease cohort (other malignant solid tumors). Patients will be recruited into the cohorts outlined in [Table 2](#).

During dose-expansion, patients will be monitored for safety according to the same criteria employed during the dose-finding phase (although events will not be considered DLTs during dose-expansion). Additionally, 4 cycles of safety information are required prior to opening the initial dose-expansion cohorts. If during the treatment period, $\geq 33\%$ of patients experience safety events meeting the DLT criteria defined for the dose-finding phase (see CSP section 4.1.2), even if outside of the DLT evaluation period, enrollment may be paused, and study data will be reviewed to determine whether additional monitoring or alternative dose levels or schedules should be evaluated prior to further enrollment.

Table 2 Malignant solid tumor cohorts

Dose-finding phase	
Cohort	Type of cancer
SARC-1	Osteo sarcoma or Ewing sarcoma

SARC-2	Rhabdomyosarcoma, non-rhabdomyosarcoma soft-tissue sarcoma, other sarcomas
NB	Neuroblastoma
STO	Other solid tumors (not represented in the other solid tumor cohorts)

Dose-expansion phase

Cohort	Type of cancer
SARCOMA	bone sarcomas: osteosarcoma or Ewing Sarcoma; soft-tissue sarcomas [\geq 40% of enrollment]: Rhabdomyosarcoma, non-rhabdomyosarcoma and other sarcomas
STO	Other solid tumors (not represented in the other solid tumor cohorts)

STO Solid tumors other.

Disease specific cohorts will not be separated into weight-based arms, but patients within the expansion cohorts will be dosed according to the appropriate weight-based RP2D determined in the arms of dose-finding cohorts.

For the SARCOMA cohort, the initial stage will allow 11 evaluable patients, to be dosed in this disease-specific cohort. If 2 or more responses are observed, additional patients will be accrued, as part of the second stage, into the corresponding expansion cohort; 15 patients will be accrued into the SARCOMA expansion cohort for a total of 26 evaluable patients. If there has been ≤ 1 objective response in either cohort, at the time that evaluable patients (11 patients) dosed in the initial stage who have been followed for at least 3 cycles and have been assessed, the cohort will be discontinued for lack of benefit.

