1.3 Number of patients

Dose-finding phase

The final sample size in the dose-finding phase will depend on the number of DLTs and on the number of dose levels to be explored. In addition, any patients not evaluable (NE) will be replaced in order to have the required number of patients evaluable at each dose level. A minimum of 12 patients is anticipated to be dosed, to enable exploration of 1 dose level in both patients weighing 35 kg and greater, and patients weighing under 35 kg. If all 3 dose levels are used at both weight-based arms, then 36 evaluable patients would be necessary to complete the dose-finding phase. If approximately 20% of patients need to be replaced due to non-evaluability, then a maximum of 45 patients will be enrolled on the dose-finding cohorts.

Dose-expansion phase

For the dose-expansion phase, the SARCOMA cohort will follow a Simon 2-stage optimal design. An ORR $\leq 10\%$ will not be considered clinically meaningful.

In the SARCOMA cohort, the Simon 2-stage design will have a type I error rate set at 0.1 (1-sided) and power of at least 85%. Based on the assumption that the ORR for the null hypothesis is 10% and the true ORR for the SARCOMA cohort is 30%, then the SARCOMA cohort will require a total of 26 evaluable patients (with the requirement that $\geq 40\%$ of the patients enrolled must have soft-tissue sarcomas), with 11 evaluable patients required in the first stage. If fewer than 2 confirmed responses are observed in the first 11 evaluable patients, then the cohort will be closed for lack of benefit. If 2 or more responses are observed out of the first 11 evaluable patients, then an additional 15 evaluable patients will be enrolled, for a total of 26 evaluable patients.

For a cohort that enrolls the maximum evaluable patients for that particular cohort (26 in the SARCOMA cohort), if fewer than 5 responses are observed out of the maximum total of evaluable patients, then no further investigation of that cohort will be done; if 5 or more responses are observed out of the maximum total of evaluable patients, then the null hypothesis will be rejected for this cohort and further investigation will be warranted.

The STO cohort is planned to recruit 10 evaluable patients. This sample size is based on practical, rather than formal considerations, as no formal hypothesis testing is planned for this cohort.

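### SAP 1.3 closes SARCOMA Stage 1 on confirmed responses but expands it on responses, and the 3-cycle minimum does not always leave time to confirm one

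*Protocol*

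**What the plan says.** **The closing rule.** In protocol 4.1.4, with at most one objective response when the 11 evaluable Stage 1 patients "followed for at least 3 cycles have been assessed, the cohort will be discontinued for lack of benefit". The synopsis (1.2) applies the rule once the patients "dosed in the initial stage have been followed/assessed for at least 3 cycles, the cohort will be discontinued for lack of benefit", and SAP 1.2 to patients "who have been followed for at least 3 cycles and have been assessed, the cohort will be discontinued for lack of benefit". None of the three uses the word confirmed or mentions a response awaiting confirmation. Protocol 9.2 also speaks only of responses.

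**SAP 1.3.** The closing sentence begins "If fewer than 2 confirmed responses are observed in the first 11 evaluable patients". The expansion sentence that follows begins "If 2 or more responses are observed out of the first 11 evaluable patients".

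**What counts as a response.** Protocol 9.4.1.2 and SAP 3.2.1 count a CR or PR only if a scan at least 4 weeks later confirms it. SAP 5 applies the SAP derivations to the Data Review Committee (DRC) analyses.

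**Scan timing.** Protocol Table 2 states: "On-study efficacy assessments occur every 8 weeks ± 1 week (always relative to the date of first dose". Its footnote u adds: "Confirmatory scans will be required". Neither gives a date for the scan that confirms a response, and section 8.1 times a confirmatory scan only for progression. Unscheduled scans count (protocol 9.4.1.1, SAP 3.1). SAP Table 3 explains the 3-cycle minimum as room for a confirmatory scan 4 weeks after the first one.

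**Design target.** Protocol 9.2 sets a "type I error rate set at 0.1 (1-sided) and power of at least 85" percent, for response rates of 10% and 30%.

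**The concern.** Two things do not fit together. First, one confirmed and one pending response satisfy both the closing and the expansion sentence of SAP 1.3, so this go/no-go rule gives two answers for one data pattern. Second, the minimum follow-up does not always achieve what SAP Table 3 says it is for, because part of the permitted window for the first scan leaves less than 4 weeks before the end of cycle 3.

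At stake is a closure for lack of benefit when a response that would have carried the cohort into Stage 2 has been seen but cannot yet be counted. The design has little slack to absorb that: its exact power is barely above the stated minimum.

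**Working it through.** **1. The plan's own design.** Inputs from protocol 9.2: 11 patients in Stage 1, close at 1 or fewer responses, 15 more patients, reject at 5 or more of 26.

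- Closure at a 30% rate: 0.7^11 + 11 × 0.3 × 0.7^10 = 0.0198 + 0.0932 = 11.30%.
- Power: sum over x = 2 to 11 of P(Bin(11, 0.3) = x) × P(Bin(15, 0.3) ≥ 5 − x) = 85.16%.
- Type I error, same sum at 10%: 8.65%.

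A search for the Simon optimal design at one-sided 0.10 and 85% power returns the same boundaries (1/11, 4/26). The plan's figures are reproduced, with 0.16 percentage points of power to spare. (The 5% test level in protocol 9.1 and SAP 4.1 is a separate matter.)

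**2. Day count from first dose.** Cycles last 28 days (protocol 1.2).

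- Minimum follow-up: 3 × 28 = day 84.
- First on-study scan: 56 ± 7 = days 49 to 63, which is 15 permitted days.
- First response on days 49 to 56 (8 days): confirmable from days 77 to 84, in time.
- First response on days 57 to 63 (7 days): confirmable from days 85 to 91, 1 to 7 days late.
- Next scheduled scan: 112 ± 7 = days 105 to 119. Nothing is scheduled in between, so confirmation by day 84 needs an unscheduled scan even when the first scan was on time.

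**3. Effect on closure and power.** The documents give neither of two inputs, so both are assumed: k, the number of the 11 patients at minimum follow-up when the decision is taken, and c, the share of their responses already confirmed. A pending response is not counted at the look but counts at the final analysis if the cohort continues.

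For k = 1 a pending response is decisive only if exactly one of the other 10 patients has responded:

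- P(exactly 1 of 10) × 0.3 = (10 × 0.3 × 0.7^9) × 0.3 = 0.1211 × 0.3 = 0.0363.
- Added closure = 0.0363 × (1 − c).
- Lost power = added closure × P(Bin(15, 0.3) ≥ 3) = added closure × 0.873.

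Schedule-tied case: first scans spread evenly over the 15 days and a rescan exactly 28 days later give c = 8/15.

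- Added closure = 0.0363 × 7/15 = 1.69 points; closure = 11.30 + 1.69 = 12.99%.
- Lost power = 1.69 × 0.873 = 1.48 points; power = 85.16 − 1.48 = 83.68%.

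Power stays at 85% only if (1 − c) × 0.0363 × 0.873 ≤ 0.0016, that is, c of about 0.95 or more.

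Range at a 30% rate, closure / power:

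| | c = 1 | c = 8/15 | c = 0 |
|---|---|---|---|
| k = 1 | 11.3% / 85.2% | 13.0% / 83.7% | 14.9% / 82.0% |
| k = 2 | 11.3% / 85.2% | 14.9% / 82.0% | 19.6% / 77.8% |
| k = 3 | 11.3% / 85.2% | 17.1% / 80.0% | 25.5% / 72.3% |

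The column c = 0 corresponds to confirmation only at the next scheduled scan. With a 28-day rescan, a second patient is exposed only if treated less than 91 − 84 = 7 days before the last one, and at day 84 + d has c = (8 + d)/15. The k = 2 and k = 3 entries under c = 8/15 are therefore upper limits.

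**4. Type I error.** At a 10% rate, k = 1 and c = 8/15 give 8.32% against 8.65%. It falls, because the effect is extra closure.

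**The case against.** The strongest reply is that the plan sets no look at day 84. Every version of the rule makes 3 cycles a minimum. Protocol 9.6 and SAP 5 describe ongoing evaluation of response in the first 11 patients, and protocol 9.6.1 leaves expansion or closure to DRC consensus. Cycles can also be delayed while scans stay tied to the first dose, so 3 cycles may run past day 84. With a 28-day rescan and a review at day 91, nothing is lost. All of this stands. A reader might infer that the plan will close the cohort on a pending response, or that its true power is the lowest entry in the table. The documents support neither: they permit waiting, and they give no k, c or review date. What remains is that they permit waiting without requiring it.

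A second reply is that SAP 1.3 means confirmed in both sentences, since the primary endpoint is confirmed response and SAP Table 4 labels it so. That is the likely intent. It removes the double answer but not the second problem: a pending response then scores as none, and no supplied text says that the decision waits for it.

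A third reply is that SAP 5 leaves details to the DRC charter, and response criteria sit in protocol Appendix E. Neither is in the supplied text, and either may settle the point. It is therefore not established that the plan as a whole lacks the rule, only that the protocol body and the SAP do not state it or point to where it is stated.

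**Conclusion.** The point holds as an inconsistency in the Stage 1 rule with a modest effect; its severity is minor to moderate. Two parts need no assumption: SAP 1.3 uses different terms for closing and expanding, and 84 days cannot confirm a response first seen on 7 of the 15 permitted scan days. The size does rest on assumptions. With one patient at the minimum, evenly spread first scans and a 28-day rescan, a pending response is decisive in 1.7% of looks at a 30% rate, and power goes from 85.2% to 83.7%. That is below the stated minimum, partly because the design had only 0.16 points to spare. Responses first seen at week 16 are not modelled. The result does not call for a later look for all patients, a larger sample or a different boundary.

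**What to change.** In protocol 1.2, 4.1.4 and 9.2 and SAP 1.2 and 1.3, write confirmed response in both the closing and the expansion sentence. Add one sentence: the cohort is not closed while CRs or PRs pending confirmation among the 11 evaluable patients could bring the confirmed count to 2, and the decision waits until each is confirmed or refuted. If the DRC charter already says this, cite it in 4.1.4 instead. Reconcile the explanation in SAP Table 3 with the Table 2 schedule and footnote u, so that it is clear when a response is expected to be confirmed. No additional scan is needed.

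The cost is wording, plus a wait only when a pending response is decisive. In the schedule-tied case that is 1.7% of looks at a 30% rate and 1.8% at 10% (closure 69.7% to 71.5%), so futility stopping is almost unaffected. If confirmation comes only at the next scheduled scan (k = 1, c = 0), it is 3.6% and 3.9%. Pending responses that are later refuted would add some waits. For a week-8 response the wait beyond day 84 is up to 91 − 84 = 7 days with a 28-day rescan, or 105 − 84 = 21 to 119 − 84 = 35 days to the next scheduled scan. For a response first seen at a later 8-weekly scan it is at most about 10 weeks (8 weeks plus both 1-week windows).
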